3.2 Overview of the interventions

SHIELD intervention. The SHIELD intervention is based on social cognitive theory, which posits that positive behavior change requires knowledge and skills to increase behavioral capability, development of self-efficacy to increase the belief that one can achieve the desired outcomes, and social support to provide positive reinforcement and develop positive outcomes expectations.⁴⁶ We developed a modular program for AGYW that increases knowledge, skills, and self-efficacy to engage along the HIV prevention and care continuum, and a program for family members (up to four participants in addition to the AGYW; 10 years and older) to increase social support. To reflect AGYW's evolving cognitive and decisional capacity, judgement, emotional development, risk, and health-seeking behaviors, intervention content for both AGYW and families were tailored for five distinct groups to reflect development stage and

AGYW's HIV status. Content areas were adapted from existing evidence-based interventions, such as Stepping Stones^{30,31} and Families Matter!^{47,48} based on CAB and YAB input and formative research with AGYW, caregivers, and community leaders. Modules address HIV prevention and treatment, general wellness and SRH, approaches to combat stigma and discrimination, and skills for better communication, and include new content on health service availability and access to increase self-efficacy in seeking health care services. SHIELD educational materials were pre-tested. The SHIELD sessions will be offered to AGYW and their families in the 4 communities randomly assigned to intervention arms. The AGYW in the usual care arm will receive one education session focused on stigma and HIV care. SHIELD education session content is presented in **Exhibit 1** for the AGYW sessions and **Exhibit 2** for the family sessions. We have noted content that will be included in core sessions along with content that will be included in the basic education provided to the control group participants. The core sessions will be provided to all participants in the intervention communities while all other sessions will be optional content for future meetings within the intervention communities.

Exhibit 1. SHIELD Content Areas for Adolescent Girls and Young Women Program

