| AGYW and Families | 
 1. What you see in me (All) 2. Making puberty easier (parents of AGYW ages 10-12) 3. HIV, AIDS and STIs- Myth or Fact (All)* 4. Helping children express their feelings (ages 10-12) 5. Taking responsibility for pregnancy: Community responsibility (ages 13-24)* | 
 1. Non-verbal communication (All) 2. Sharing information with family members: challenges and possibilities (HIV+ ages 16-24)* 3. Providing emotional support after a child learns that you or they are HIV positive (All) 4. Analyzing stigma against AGYW (All)* |

* Indicates core topic area

IWC Clinic

The Integrated Wellness Care (IWC) clinic for AGYW will be established in 2 randomly selected health centers participating in this study communities. The clinic will provide integrated HIV and sexual and reproductive health services to both participating HIV-/u and HIV+ AGYW facilitated by a trained nurse. Specifically, the IWC clinic will offer:

- HPV vaccination
- HIV testing & counselling
- ART adherence counselling (HIV+ AGYW)
- STI services information
- Family planning, including counselling, initiation of contraception, services related to current contraception, and pregnancy testing and counselling.
- Information on cervical cancer screening
- Referrals for services, such as mental health, gender-based violence, STI testing, cervical cancer screening, and other health services as needed

All services will be provided based on the standard of care guidelines and delivered by a trained nurse. IWC components and data collection was tested during the pilot-testing phase. In addition, selected staff at the health centers with the IWC clinic will receive stigma training to ensure team-based care is available for AGYW who are referred from the IWC clinic to received services in other departments at the health center. The training section includes four modules (2-hour session for each) that experienced trainers will deliver to give staff the skills to create a stigma-free health facility.^{29,30}

Caregiver and provider support for AGYW. We will include caregivers who will participate with AGYW in the SHIELD family sessions. We will identify one caregiver for each participating AGYW in the 6

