The sample size was calculated assuming conventional specifications (power = .80, alpha = .05, two-sided tests) and based on the primary endpoints. The sample sizes were determined to allow for the detection of a 15–percentage point improvement in the primary endpoints, our minimum threshold to consider the intervention to be successful. For the HIV-/u cohort, the current rate of HIV testing is estimated to be about 40%. With a sample size of 200 (each of the three cohorts), The study team will be able to detect a 13 to 14% difference, and even with a loss of 10% of the cohort during follow-up (the grant team achieved a 90% retention rate at 12 months in a recent study of AGYW),²⁸ the study team

will still have the statistical power for a minimum detectable difference in HIV testing of 15%. For the HIV+ cohort, viral load suppression is estimated to be 70 to 75% among AGYW. With a sample size of 175 per cohort, the study team will be able to detect a minimum difference of 15% even with a 10% loss to follow up. See **Exhibit 3** for details on sample size included in the cluster randomized trial.

Exhibit 3. Experimental design and sample sizes*

Post-intervention data collection: We will conduct one post-intervention survey with AGYW at about 24-months from study initiation (approximately 12 months after intervention completion).

Research Protocol

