Assess efficacy of the multilevel interventions (hypothesis testing). Cluster randomization study design and interventions. We propose a cluster randomized study implemented in the six selected geographic zones in Lusaka, each served by a government-operated clinic providing HIV and cervical cancer screening services. Zones, with their respective clinics, will be randomized into three groups (zones with IWC clinics and SHIELD intervention, zones with only SHIELD intervention, and control zones with no IWC clinic or SHIELD interventions. AGYW in the control zones will be offered one education session on HIV prevention and treatment) to assess the impact of offering IWC clinics coupled with the SHIELD intervention compared to the standard of care (see Exhibit 1 above). The study team will also evaluate whether a similar impact can be achieved with control clinics when the SHIELD intervention is offered in the community. The SHIELD intervention, as described in Section 3.2, will begin with training sessions for AGYW and their families. This will be followed by PN-facilitated youth clubs that will meet about once a month during the 12-month study timeframe. Two-four PNs will be assigned to each clinic zone with the SHIELD intervention, and one-two PN each will be assigned to the two control clinic zones to assist with data collection and follow-up activities. The PNs in zones with the IWC clinics will also serve as community liaisons to support clinic-community linkages. The health centers in which the **primary endpoint for the HIV/u cohort** is the proportion with any HIV testing at 12 months. **For the HIV+ cohort, we plan to assess the primary endpoint:** viral load suppression, measured as proportion with undetectable viral load at 12 months. The secondary endpoints are the proportion with decrease in HIV risk behavior, repeat HIV testing (each 6-month period), HIV infections diagnosed through voluntary HCT, linkages to HIV care, and adherence to ART. We will also conduct a targeted 6-month post-intervention data collection after the end of the 12-month intervention period. See **Exhibit 4** for endpoint definitions and biological, self-report, and clinic audit measures collected at 6- and 12-month follow up. To assess the impact of the SHIELD intervention on the mediating outcomes, the study team will collect data from AGYWs across all six clinic zones at baseline and at 6- and 12- month follow-up. The study team will also track health care service use by conducting clinic audits at all six clinic sites. We plan to retain the intervention cohort for a maximum of 24 months total to allow for initiation of the intervention and follow-up activities (12 months of intervention and follow-up after intervention completion).

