Hypotheses on intervention effect. The study team will test the following hypotheses: (1) HIV-/u AGYW from zones with IWC clinics and who receive SHIELD intervention will have higher HIV testing than AGYW in zones without the IWC clinics (including those receiving SHIELD intervention with usual care clinics); (2a) HIV+ AGYW from zones with IWC clinics and who receive SHIELD intervention will have higher viral load suppression (2b) than AGYW in zones without the IWC clinics (including those receiving SHIELD intervention with usual care clinics); (3) HIV+ AGYW from zones with IWC clinics will receive more-timely linkages to care than AGYW in zones without a IWC clinic; (4) AGYW from zones who receive SHIELD intervention will have improved self-efficacy (4a) and social support (4b), and reduced HIV risk behaviors (4c) compared to AGYW from zones not receiving the intervention.

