Analysis of hypotheses. The **testing of the primary hypotheses** will be done by intent to treat, and the study team will examine the effects across the three randomization groups. Given the need to consider the influence of the cluster randomization by zone, The study team will use generalized estimating equation (GEE) models to estimate the effects of the randomization groups and will assess the need to apply small sample correction using approaches suggested by the NIH Health Care Systems Collaboratory Biostatistics and Design Core.⁵⁹ If the Hausman assumption of correlation between the random and fixed effects is violated, then The study team will include fixed effects representing cluster identification. The study team will adjust for baseline covariates, including sociodemographic factors and behavioral risks, should the initial descriptive analyses suggest differences in the distribution of these factors across study randomization groups. The study team will also explore the use of propensity scores to control for systematic differences between the groups. In further analyses, the study team will examine the potential mediating and moderating roles of key behavioral, social, and structural factors hypothesized to influence HIV testing and adherence along the HIV care continuum (e.g., social support; self-efficacy).. The study team will test the “dose” of the SHIELD training received as a covariate in these models. **Secondary analysis** will follow the same approach. As appropriate, the study team will perform analyses separately or pooled together for the HIV+ and HIV-/u cohorts. A key aspect of interest in this study is the developmental stage of the AGYW; using age as a proxy in our multivariate analysis, the study team will determine the differential effect of the IWC clinic and SHIELD intervention on outcomes reported by HIV status (see Exhibit 1 for groupings). In subsequent analyses, the study team will also consider both medium-term outcomes within the first 6 months after study enrollment and changes at any point during the 12-month follow-up period to assess longer-term outcomes. Additionally, for measures where we have baseline, 6-month and 12-month follow-up data (for example, self-efficacy, and other mediating outcomes for AGYW), the study team will perform difference-in-difference analysis, which will allow for comparisons between and across the study arms. The study team will also report all mediating factors, and 'IWC clinic utilization metrics stratified by age and HIV status to facilitate subgroup analysis. Importantly, the changes along the HIV care cascade, from HIV testing, linkage to care, ART adherence, and viral load suppression, will be documented to identify potential differential impacts of the interventions. This analysis is critical to assist in further tailoring the SHIELD training and IWC clinic services.

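### The 80% power claimed for a 15-point gain in HIV testing is that of an individually randomised trial; with two zones per arm it holds only at an ICC up to about 0.0007 pairwise, or 0.0045 for 2 v 4 zones

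*Combined protocol and SAP*

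**What the plan says.** The sample-size paragraph of section 3.3 sets power at .80 and alpha at .05, two-sided. It sizes the trial for a 15-point improvement in the primary endpoints, described as "our minimum threshold to consider the intervention to be successful".

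- **HIV-/u cohort:** about 40% currently tested; 200 per arm is said to detect 13 to 14 points. After 10% loss the team "will still have the statistical power for a minimum detectable difference in HIV testing of 15" percent.
- **HIV+ cohort:** suppression of 70 to 75%. "With a sample size of 175 per cohort, the study team will be able to detect a minimum difference of 15" percent, again allowing for 10% loss.

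The design is described elsewhere. Under Research Protocol: "We propose a cluster randomized study implemented in the six selected geographic zones in Lusaka", split into three groups, with two control zones. Section 3.2 adds "The SHIELD sessions will be offered to AGYW and their families in the 4 communities randomly assigned to intervention arms", and the IWC clinic "will be established in 2 randomly selected health centers". That makes two zones per arm.

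Hypothesis 1 states that AGYW in IWC zones "will have higher HIV testing than AGYW in zones without the IWC clinics (including those receiving SHIELD intervention with usual care clinics"), a comparison of two zones with four. Research Protocol also describes IWC plus SHIELD against standard of care, which is two zones with two.

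The analysis section chooses GEE with the words "Given the need to consider the influence of the cluster randomization by zone", and leaves open whether a small-sample correction is needed.

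**The concern.** The analysis section accepts that outcomes within a zone are correlated, but the sample-size paragraph gives no ICC, design effect or cluster degrees of freedom. Exhibit 3, to which it refers for details, is not shown in the copy reviewed. The HIV-testing figures can still be checked by themselves: if they already match a calculation with independent participants, they hold no allowance for clustering, whatever Exhibit 3 says.

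HIV testing is a primary endpoint, and 15 points is the plan's own bar for success. If real power at 15 points is well below 80%, a non-significant result is weaker evidence against a 15-point effect than the plan implies. The results are meant to inform government policy (section 3.3.5) and possible national scale-up. GEE can give standard errors that respect clustering, but it does not restore lost power.

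**Working it through.** **Inputs from the documents.** Two-sided alpha .05; power .80; target 15 points; HIV testing 40%, 200 per arm; viral suppression 70 to 75%, 175 per arm; 10% loss; six zones, two per arm. Assuming equal zones, retained participants per zone are m = 200 × 0.9 / 2 = 90 (HIV-/u) and 175 × 0.9 / 2 = 78.75 (HIV+).

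**Step 1: reproduce the plan's figure.** With independent participants, the detectable difference d solves

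d = (1.960 + 0.842) × √{[p0(1 − p0) + (p0 + d)(1 − p0 − d)] / n}, with p0 = 0.40.

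- n = 200: d = 13.85 points (13.94 with pooled variance). The plan says 13 to 14.
- n = 180: d = 14.59 points (14.70 pooled). The plan says 15.

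Both stated figures match a design effect of 1.

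**Step 2: the slack at 15 points (40% v 55%).**

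- Pairwise, 180 v 180: SE = √(0.2475/180 + 0.24/180) = 0.0520. 0.15/SE = 2.882, so power = Φ(2.882 − 1.960) = 82.2%. Largest design effect keeping 80%: (2.882/2.802)² = 1.06.
- 2 v 4 zones, 180 v 360: SE = √(0.2475/180 + 0.24/360) = 0.0452. 0.15/SE = 3.320. Largest design effect: (3.320/2.802)² = 1.40.

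**Step 3: convert to an ICC.** Design effect = 1 + (m − 1) × ICC, with m = 90.

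- Pairwise: ICC ≤ 0.0585/89 = 0.00066 (0.0005 with pooled variance). The between-zone SD of true rates, √(ICC × 0.4 × 0.6), is then at most about 1.3 points.
- 2 v 4: ICC ≤ 0.404/89 = 0.0045, an SD of about 3.3 points.

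**Step 4: power over an assumed ICC range.** The documents give no ICC, so 0.005 to 0.02 is an assumption. Normal critical values; all comparison zones at the control rate; MDD = minimum detectable difference at 80% power.

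| HIV testing, 40% control | ICC 0.005 | 0.01 | 0.02 |
|---|---|---|---|
| Design effect | 1.445 | 1.89 | 2.78 |
| Pairwise: power at 15 points | 67% | 55% | 41% |
| Pairwise: MDD (points) | 17.5 | 19.9 | 23.9 |
| 2 v 4: power at 15 points | 79% | 68% | 51% |
| 2 v 4: MDD (points) | 15.2 | 17.3 | 20.8 |

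**Step 5: the HIV+ cohort.** With 157.5 retained per arm, independence gives 13.2 points (70% control) or 12.2 (75%) against the stated 15.

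| HIV+ (70% / 75% control) | Largest ICC for 80% | Power at ICC 0.01 | Power at ICC 0.02 |
|---|---|---|---|
| Pairwise | 0.004 / 0.008 | 68% / 76% | 53% / 61% |
| 2 v 4 | 0.012 / 0.019 | 83% / 91% | 68% / 78% |

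**Step 6: two features that make these figures generous.**

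- *Few clusters.* With a t reference, 80% power for HIV testing is not reached even at ICC 0. Pairwise power is 37% on 2 df and 50% on 3 df; 2 v 4 power is 61% on 3 df and 70% on 4 df. The plan fixes no degrees of freedom, so these are examples (6 zones − 3 arms = 3; 4 − 2 = 2; 6 − 2 = 4).
- *SHIELD-only effect.* The 2 v 4 figures assume SHIELD alone does nothing. As an illustration, if SHIELD-only zones reach 45%, the pooled comparator is (40 + 45)/2 = 42.5% and the contrast falls to 12.5 points. Power is then 79% at ICC 0 and 52% at ICC 0.01.

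**The case against.** The arithmetic in the plan is correct for the calculation it performs; what is missing is a design assumption. The size of the shortfall depends on an ICC that the documents do not give. At 0.005 the 2 v 4 contrast has 79% power, close to the claim, and 2 v 4 is the contrast that hypothesis 1 states. Section 3.3.4 plans to select similar clinics and assess baseline differences before randomisation, and the analysis allows covariate adjustment; both could reduce variation between zones. Exhibit 3 might state an ICC, and the HIV+ figure leaves room for a pairwise design effect of 1.34 to 1.63, so an allowance there cannot be ruled out. Section 3.1 speaks of the trial in the past tense, so a revised power statement may change no design decision. And no passage says that a non-significant result will be called a failure.

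Part of this stands. The HIV+ claim is conditional rather than wrong, and the pairwise limit must not be presented as the only one. But the ICC limits in Step 3 do not depend on the assumed range. Exhibit 3 cannot put a pairwise design effect above about 1.06 into the HIV-testing figures. Similar clinics and covariate adjustment may lower the ICC, but the plan does not show that they bring it to near zero. If follow-up is complete, the statement still governs how a null result is read.

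**Conclusion.** The concern holds. For HIV testing, the stated 80% power at 15 points belongs to an individually randomised comparison. With two zones per arm it survives only to an ICC of about 0.0007 pairwise (design effect 1.06) or 0.0045 for 2 v 4 (design effect 1.40). These limits assume equal zones of 90 retained, normal critical values and, for 2 v 4, no effect of SHIELD alone. A small-sample t reference, or any benefit of SHIELD alone in the 2 v 4 contrast, lowers power further. Over an assumed ICC of 0.005 to 0.02, power runs from 67% down to 41% pairwise and from 79% down to 51% for 2 v 4. The HIV+ claim can be true, but only below an ICC that the readable text does not state. Because this concerns a primary endpoint and the plan's own success threshold, it should be corrected.

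**What to change.** In the sample-size paragraph of section 3.3, replace the unconditional claim with a short table for both cohorts:

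- power at 15 points and the MDD, for two zones per arm with about 90 and 79 retained per zone;
- an explicit ICC range, for example 0.005 to 0.02;
- both the pairwise and the 2 v 4 contrasts, with the degrees of freedom of the test to be used;
- the effect assumed in SHIELD-only zones.

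Baseline data may inform the ICC for HIV testing if testing was recorded then, but keep the range. With six zones of 100, an estimate of 0.01 corresponds to F = 1.99/0.99 = 2.01. Dividing by the F quantiles on 5 and 594 df (about 2.59 and 0.166) gives a 95% interval of roughly −0.002 to 0.10.

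Add a sentence that a non-significant result will be reported as an estimate with its cluster-adjusted confidence interval, not as failure to reach 15 points. If follow-up is complete, the same table and sentence belong in the SAP and the report.

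The cost is wording and a short calculation. No participants are added and the design does not change; the stated power becomes less favourable.

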
Exhibit 4. Tables of measures at baseline, 6 months (6m), and 12 months (12m); few measures also collected at about 24 months (24m) during the post intervention period.

| Constructs/Measures | Instrument and Specification | Source | Cohort |
|---|--|-----------------------------|---|
| Primary and Secondary Endpoints—HIV Care Continuum and HIV Risk Behavior | | | |
| HIV testing; proportion tested for HIV in the past 6 and 12 months | Abstraction tool (serologic HCT); and self-report confirmed via clinic audit; repeat HCT at 6-month intervals will be assessed | Clinic audit Self-report | HIV-/u 6m,12m Self report only at 24m |
| HIV early detection; proportion with HIV identified through voluntary testing | All participants will be tested to determine HIV status (rapid finger prick and follow-up per Zambian guidelines) | Biological | HIV-/u 12m |
| Linkage to care: proportion enrolled at an HIV clinic in ≤ 30 days; ART initiated in ≤ 90 days | Measured as days from testing HIV positive or from baseline when not on treatment (HIV+ but not on ART) | Clinic audit | HIV-/u HIV+ 6m & 12m |

| | | | |
|--|--|--------------------------------------|--|
| Adherence to ART; proportion filling prescriptions at least every 3 months | Zambian guidelines recommend dispensing 3-month supply of ART medications | Clinic audit Self-report | HIV+ 6m &12m Self-report only at 24m |
| Viral load suppression; proportion with undetectable viral load | HIV plasma viral load tests using the Roche platform | Biological | HIV+ 6m &12m |
| HIV risk behavior: proportion with delay in first intercourse, reduction in sexual partners; increases in condom use | Demographic and Health Survey and AGEP instrument (measures will be based on previous studies by grant team, including AGEP) | Self-report | HIV-/u Baseline, 6m, 12m & 24m |
| AGYW (Mediating outcomes, SHIELD intervention dose, and clinic-based services) | | | |
| Self-efficacy, social support, HIV stigma & gender roles | Tailored instrument based on supplemental survey completed at cohort recruitment | Self-report | HIV-/u & HIV+ Baseline, 6m, & 12m |
| Mental health and substance abuse | Brief assessment based on NICHD consortium common data elements | Self-report | |
| Unintended pregnancy | Tested at 12m | Urine test | |
| Education modules (AGYW & family) | Number of modules completed | Study database | Self-report at 24m |
| Youth club attendance | Number and proportion of meetings attended | | |

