| HPV vaccination | Proportion receiving 1, 2, or 3 doses (IWC clinic only) | Clinic audit & visit data collection | HIV-/u & HIV+; 6m & 12m |
| Number of clinic visits | Proportion with visits at 6m and 12m; total number of visits | | |
| SRH services provided | Family planning, sexually transmitted diseases, and condoms | | |
| Baseline Data for AGYW | | | |
| Demographics & socio-economic status | AGEP baseline instrument | Self-report | All AGYW 24m |

Trained data abstractors will obtain the information from the clinical records at baseline and during the 6- and 12-month follow-up using prespecified abstraction forms. UNC's Zambia project manager will supervise the data collection at the IWC clinics that will manage the pre-screening processes, track visits, clinical services provided, and linkages for HIV care. Specially trained staff will perform biological data collection, which will include HIV testing at 12 months for the HIV-/u group, viral load testing at 12 months for the HIV+ group, and pregnancy testing for both groups at 12 months. All data collectors will be trained, data collection will undergo continual monitoring, and fidelity to protocol specifications will be confirmed by random in-person review of supervisors' data collection. IWC clinic staff will keep detailed records to track patient visits along with information on staff time spent across various clinic activities. Data will be stored locally at secure location at Population Council offices and reviewed for data completeness. Deidentified data then will be transferred securely to RTI and archived in secure,

password-protected servers. RTI staff will conduct further data quality review, produce reports, and develop analytic files.

SHIELD intervention exposure. Using attendance information entered in the study database, the study team will quantify the number of SHIELD education sessions AGYW and family members attend and the number of youth clubs AGYW attend. This will allow us to calculate the amount of exposure to the intervention (dose) for each participant. This dose estimate will be used as a covariate in sub analyses that examine the dose-response of the interventions on outcomes.

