Loss of confidentiality. There is a risk of loss of confidentiality for AGYW around study participation; HIV status; ART use; or data reported in project questionnaires. The intervention activities also carry a risk of participant disclosure of personal information during group activities such as the SHIELD intervention youth clubs, and during participant tracking for follow-up. It is also possible that other people may find out that participants have taken part in this research, and as a result, participants may be treated unfairly, discriminated against, or face problems being accepted by their families, communities, or both.

HPV vaccination. The World Health Organization recommends HPV vaccination. The Global Advisory Committee on Vaccine Safety has systematically investigated the HPV vaccine and found it to be safe. As with any vaccination, some people may have some side effects. These are usually mild and include a sore arm from the shot, fever, headache, or nausea. Brief fainting spells can happen immediately after any medical procedure, including vaccination.

Discomfort with learning HIV status or with interview topics and questionnaires. AGYW participants may experience psychological discomfort upon learning their HIV or pregnancy status. Sensitive interview topics related to HIV status, ART use, stigma, reproductive health, or sexual behavior may make some participants feel uncomfortable, worried, or embarrassed.

There is little to no risk for other participants, including clinic staff and stakeholders. All of the questions we will ask relate to their daily work as clinic staff or community leaders. Additionally, clinic staff and other government or private stakeholders who participate in IDIs will not be asked any sensitive questions. All responses will be de-identified and only reported in aggregate form. Clinic administrators will not have access to individual staff member responses.

COVID-19-associated risks

The COVID-19 pandemic may present health risks to both participants and the staff who engage with participants in the clinic and community setting. These health risks are significant but are not unique to our study. COVID-19 may pose a larger risk during group meetings, such as the SHIELD educational sessions, than for one-on-one contact. The project team is closely monitoring COVID trends in Zambia and has detailed our risk mitigation strategy in the below section.

Potential benefits

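### The 30-day linkage and 90-day ART windows run past the last clinic audit for HIV-/u girls diagnosed late in the year or by the 12-month study test

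*Combined protocol and SAP*

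**What the plan says.** All of this is in the combined protocol and SAP, section 3.3.

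- **Definition.** The linkage row of Exhibit 4 reads "Linkage to care: proportion enrolled at an HIV clinic in ≤ 30 days", and asks that ART be "initiated in ≤ 90 days". The time origin is "Measured as days from testing HIV positive or from baseline when not on treatment (HIV+ but not on ART".
- **Source and time points.** The row names clinic audit as its only source. Its cohort and timing entry is "HIV-/u HIV+ 6m & 12m", with no 24-month entry.
- **Study test.** The HIV early detection row says "All participants will be tested to determine HIV status (rapid finger prick and follow-up per Zambian guidelines". The text after Exhibit 4 places this test at 12 months for the HIV-/u group.
- **Abstraction schedule.** "Trained data abstractors will obtain the information from the clinical records at baseline and during the 6- and 12-month follow-up".
- **Use of the endpoint.** Linkage is a secondary endpoint and carries hypothesis 3: "HIV+ AGYW from zones with IWC clinics will receive more-timely linkages to care than AGYW in zones without a IWC clinic".

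The plan does not say how an incomplete 30- or 90-day window is scored, or whether a positive 12-month study test enters the linkage endpoint.

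**The concern.** An outcome defined over 30 or 90 days can be scored only if records are read for that long after the clock starts. Here the last scheduled reading of the records falls at the same visit as the test that starts the clock for study-detected cases, and less than 90 days after any other diagnosis made in the last quarter of the year.

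Two things are at stake. First, if a girl whose window was cut off is counted as not linked or not started, the proportion is too low. Second, hypothesis 1 expects more testing in IWC zones. If that happens, more of the positives in the other zones could first appear at month 12, where linkage cannot be observed. Scoring them as failures would then lower the comparator, and leaving them out would leave mainly voluntary testers there. Either choice could distort hypothesis 3.

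**Working it through.** The documents give no rate, yield or sample size for linkage, so there is no plan figure to reproduce. The check is calendar arithmetic followed by illustrations under stated assumptions.

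**Inputs from the documents:** windows of 30 and 90 days; last clinic audit at 12 months; study test of the HIV-/u cohort at 12 months (all Exhibit 4 and the text after it); about 600 HIV-/u girls and 10% loss (section 3.3, recruitment and sample size). **Assumption:** the 12-month audit closes at day 365.

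**Step 1: last positive test with a complete window.**
- Enrolment: 365 − 30 = day 335, about month 11.0.
- ART start: 365 − 90 = day 275, about month 9.0.
- Positive study test at day 365: 365 − 365 = 0 days observed.
- To complete both windows for that test: 365 + 90 = day 455, about month 15.

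**Step 2: who is not affected.** HIV+ girls not on ART at baseline start the clock at day 0. Their windows close at days 30 and 90, before the 6-month audit.

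**Step 3: share of voluntary diagnoses with a cut-off window**, if they are spread evenly over 12 months (assumption).
- Enrolment: 30/365 = 8.2%.
- ART start: 90/365 = 24.7%.

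**Step 4: share of all new diagnoses with a cut-off window.** Let s be the share first found by the 12-month study test (not given, so a range is used). The incomplete share is s + (1 − s) × 30/365 for enrolment and s + (1 − s) × 90/365 for ART start.

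| s | Enrolment incomplete | ART incomplete |
|---|---|---|
| 25% | 31% | 43% |
| 50% | 54% | 62% |
| 75% | 77% | 81% |

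**Step 5: number of girls.** Retained: 600 × 0.90 = 540. If the study test finds 0.5% to 5% positive (assumption), that is 540 × 0.005 = 2.7 to 540 × 0.05 = 27, or about 3 to 27 girls with essentially no observed window.

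**Step 6: understatement among voluntary diagnoses if truncation counts as failure.** Take a true 90-day ART start of 80% (assumption).
- Starts spread evenly over 90 days: 0.80 × (1 − 0.247 × 0.5) = 0.70.
- Starts spread evenly over 30 days: 0.80 × (1 − 0.082 × 0.5) = 0.77.

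The loss is about 3 to 10 points, depending on how quickly girls start.

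**Step 7: how a difference between arms could arise.** Among newly diagnosed girls, with study-test positives scored as failures, the observed proportion is v × (1 − s), where v is the figure from step 6. Two arms with the same v but different s differ by v × (difference in s). A 10-point difference in s gives 0.70 × 0.10 = 7.0 to 0.77 × 0.10 = 7.7 points with no true difference. This is before dilution by the HIV+ girls timed from baseline.

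**The case against.** **Much of the endpoint is fully observed.** Hypothesis 3 speaks of HIV+ girls, and those not on ART at baseline have complete windows. The Literature Review says 78% of diagnosed youth are in treatment. If 5% to 22% of the 525 HIV+ girls are off ART (the lower end is an assumption), that is 26 to 115 girls. Give them the same 80%. Add 6 to 18 study-test positives scored as failures (1% to 3% of 600, an assumption) and as many earlier diagnoses at 70%. The pooled ART figure then runs from (26 × 0.80 + 18 × 0.70)/(26 + 18 + 18) = 54% to (115 × 0.80 + 6 × 0.70)/(115 + 6 + 6) = 76%. This stands. A reader who looks only at new diagnoses might infer that the overall figure collapses, but the definition itself brings in this unaffected group.

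**The plan does not put study-test positives into the endpoint.** The universal test sits in the early detection row, whose measure concerns voluntary testing, so it may serve only that measure. Limiting linkage to diagnoses made during the intervention is a defensible reading. This stands, but the plan does not state it, and ART windows of voluntary diagnoses after month 9 would still be cut off.

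**Later data collection exists.** Section 3.3 mentions a targeted collection 6 months after the intervention and a survey at about 24 months. The content of the first is not stated, and Exhibit 4 assigns linkage to neither. The 12-month abstraction also has no fixed closing day, so some later days may be caught. No 90-day extension is planned.

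**Late diagnoses are not lost altogether.** A reader might infer that they go unseen. Enrolment or ART start before the audit is recorded, and only the rest of the window is missing. Section 1.1 says that Zambia has adopted a test-and-start approach, which makes the shorter start times in step 6 plausible.

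**Participant safety.** The Risks section notes that "AGYW participants may experience psychological discomfort upon learning their HIV or pregnancy status", and a reader might infer that study-diagnosed girls are left without care. The documents do not support that. Exhibit 4 provides for follow-up under national guidelines, Steps to Minimize Risks provides referrals and DSMB review of social harms, and section 3.3.4 gives each girl a peer navigator. What is missing is a scheduled outcome measurement, not a care pathway.

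**Conclusion.** The mismatch holds, for newly diagnosed HIV-/u girls only. Given an audit that closes at 12 months, it is certain that ART windows opening after about month 9 and enrolment windows opening after about month 11 are incomplete, and that windows opening at the 12-month test are almost wholly unobserved. No other section resolves this. The missing-data text in section 3.3.4 deals with nonresponse and attrition, not with windows cut short by the audit date.

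The consequence is conditional. The endpoint is understated if truncated cases are scored as failures, which the plan neither requires nor rules out. Bias between arms also needs the arms to differ in how many positives first surface at month 12. A reader might infer an established bias against the control zones; the documents give no yield by arm. With 6 to 18 study-test positives in all (the assumption used above), an even split would be about 2 to 6 per arm, in two zones per arm. The net size is therefore unknown, and the percentages in the working illustrate it and do not estimate it. The primary endpoints and the sample size are not affected.

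**What to change.** For the linkage row of Exhibit 4 only:

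1. Extend clinic-record abstraction to 90 days after the 12-month test for HIV-/u participants who are positive at that test or were diagnosed after month 9, and add this time point to the row. Section 3.1 is written in the past tense. If follow-up has ended, obtain the same dates retrospectively from clinic records.
2. Score each 30- or 90-day outcome only when its full window has been observed. Decide this from the date of the positive test and the date the records were read, not from whether an event was found. Otherwise early successes would be kept and unfinished windows dropped.
3. Report voluntary diagnoses and 12-month study-test diagnoses separately, so that a difference between arms in the mix is visible.

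The cost is one small extra abstraction at six clinics that are already audited, for a small group of girls, and a linkage result about three months later. Month 15 lies within the 24 months for which the cohort is to be retained. No new participant visit is needed.
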